#### 2.2 Subgroup Objectives

The Aqueous-PREP trial will also explore the possibility of differential treatment effects of the pre-operative antiseptic skin solutions among clinically important open fracture subgroups. Subgroups will be defined by: i) the severity of open fracture (Gustilo-Anderson type I or II versus III); ii) upper extremity versus lower extremity open fractures; and iii) severity of wound contamination. High-grade soft tissue injury (Gustilo-Anderson type III), lower extremity open

fractures, and moderate/severe wound contamination are established predictors of SSI and reoperations from the FLOW trial.  In addition, there are known differences in patients' skin flora based on anatomic region of injury. As a result, it is likely that the study interventions may be more effective in certain subgroups. Due to its broader spectrum of antimicrobial activity, the increased effectiveness observed by Swenson *et al.*, and the possible benefits observed in the FLOW trial, we hypothesize that 10% povidone-iodine antiseptic skin solution will be associated with a larger reduction in odds for SSI and reoperation in open fracture patients with worse fracture severity, lower extremity fractures, and more severely contaminated wounds.

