## 4.4 Randomization Methods

Treatment allocation will be determined using a cluster-randomized crossover trial design. The order of treatment allocation for each orthopaedic practice (cluster) will be randomly assigned using a computer-generated randomization table. Each site will start with the initially allocated study solution and crossover to the other solution for their second recruitment period. This process of alternating treatments will repeat approximately every 2 months as dictated by the initial randomization. For sites that enroll for more than 1 year, the order of treatment allocation may be reversed after 12 months to ensure equal distribution of each treatment across each calendar month

in the study's duration (**Figure 1**). Randomization will be completed by personnel at the CEO Methods Center at the onset of the trial. Personnel from the Methods Center will notify personnel at each participating clinical site of their treatment allocation order. This will allow each participating clinical site to begin preparing for the first run-in period.

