## 4.5 Blinding

The orthopaedic team (including the study coordinators) cannot be blinded to the treatment allocation as the antiseptic solutions are visually distinguishable and these individuals need to lead the implementation of the cluster-crossover protocol at their clinical site. The Adjudication Committee Members and data analysts will be blinded to the study treatment. All interpretation of study results will initially be done in a blinded manner by developing two interpretations of the results. One interpretation will assume treatment A is povidone-iodine, the other interpretation will assume it is CHG. Once the data interpretations for each assumption are finalized, the data will be unblinded and the correct interpretation will be accepted.

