## 5.2.2 Analysis of the Study Outcomes

Adopting an ITT principle, multilevel regression models will be used. Correlation structures will be fit based on the observed between cluster and between period effects. A robust sandwich estimator will be used to analyze the primary and secondary outcomes.

For the primary outcome, SSI will be the dependent variable and the antiseptic solution (treatment group) will be the independent variable. For the secondary outcome, unplanned fracture-related reoperation will be the dependent variable and the antiseptic solution (treatment group) will be the independent variable. For both analyses, multiple imputation will be used to handle missing data.

As the optimal methods for analyzing cluster crossover trials continue to evolve, the final statistical modeling technique to be used will be determined in accordance with contemporary best practices prior to the completion of participant follow-up. A separate Statistical Analysis Plan will be developed prior to study closeout. **Table 6** below shows a summary of the study outcomes, corresponding hypotheses, and currently proposed methods of analysis.

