#### 5.2.3 Subgroup Analyses

Three subgroup analyses will be performed. The primary subgroup will be defined by the severity of open fracture (Gustilo-Anderson type I or II versus III). Secondary subgroups will include: i) upper extremity versus lower extremity open fractures; and ii) none, minimal, or surface contamination versus contamination embedded in bone or deep soft tissues. These analyses will be performed by comparing the effect estimates in both groups (interaction effect). We hypothesize that effect will differ by subgroup. These analyses will be approached and reported in accordance with best practices and guidelines for subgroup analyses. **Table 7** below shows a summary of the subgroup analysis objectives, corresponding outcomes, hypotheses, and methods of analysis.

Table 7: Summary of Subgroup Analysis Plan

Objective	Outcome		Hypothesis	Method of	
Objective	Name	Type	Hypothesis	Analysis	
Primary					
Severity of open fracture (Gustilo-Anderson Type I or II vs. Type III)	SSI / Unplanned Fracture- Related Reoperation	Binary	10% povidone-iodine will be associated with a larger reduction in odds for SSI and reoperation than CHG in more severe fractures	Interaction of treatment by subgroup	
Secondary					
Upper extremity vs. lower extremity fractures	SSI /	Binary	10% povidone-iodine will be associated with a larger reduction in odds for SSI and reoperation	Interaction of treatment by subgroup	

	Unplanned Fracture- Related Reoperation		than CHG in lower extremity compared to upper extremity fractures	
None, minimal, or surface wound contamination vs. embedded wound contamination	SSI / Unplanned Fracture- Related Reoperation	Binary	10% povidone-iodine will be associated with a larger reduction in odds for SSI and reoperation than CHG in embedded contaminated wounds compared to wounds with no, minimal or surface contamination	Interaction of treatment by subgroup

**Note:** CHG = 4% chlorhexidine gluconate; SSI = Surgical Site Infection

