## 7.2 Consent

In many cluster randomized comparative effectiveness trials, a waiver of consent is obtained from the IRB of Record. The rationale for the waiver of consent is that all patients will receive treatments that are effective and within standards of care, they will receive one of the study treatments as part of their routine care regardless of study participation, the data collection is minimal and obtained from the patient's medical records, the trial involves no more than minimal risk to the patient, and that the waiver of consent will not adversely affect the rights and welfare of the patient. Most of these concepts apply to the current trial, as the Aqueous-PREP trial is comparative effectiveness research where patients will receive one of the preoperative antiseptic skin solutions regardless of their participation in the study. Additionally, patients are not included in the decision-making process for the choice of antiseptic preparation solution, and, in most situations, they are not even aware of which solution is used. However, in contrast to many cluster randomized crossover trials, Aqueous-PREP study personnel will need to contact participants directly to collect baseline and outcome data, as this information cannot be reliably obtained from

the patients' medical records. Therefore, study personnel will obtain informed consent from patients prior to data collection. This consent process will allow study participants to be informed about the study rationale and provide consent for ongoing surveillance and data collection.

To increase enrollment and to avoid missing potential study participants, the consent process may take place up to 3 weeks post-fracture. Consultation during the study design phase with IRB members and patient advisors confirmed the acceptability of this flexible approach, where consent may be obtained after the intervention. The primary rationale for allowing consent after the intervention is consistent with the waiver of consent principles outlined above, but in addition, the patient and IRB stakeholders recognized that obtaining consent prior to the patient's first surgery could add undue decision making stress to a patient who is awaiting surgical management of a serious extremity injury; allowing consent after their surgery would likely facilitate an improved consent process.

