The consent process will typically take place in the patient's hospital room or in the outpatient fracture clinic, either before or after the patient has had surgery(ies) to manage their open fracture. If the patient is unable to provide informed consent (e.g., due to their injury, language restrictions) within 3 weeks of their fracture, informed consent will be obtained from their proxy. In addition, if a patient has been discharged from hospital prior to being invited to participate in the study, a delegated member of the clinical care team may obtain their consent by telephone, as approved by the IRB of Record.

To obtain informed consent, delegated study personnel should follow the below procedures:

- Present study information in a manner that is understandable to the potential participant/proxy.
- Discuss the study with the potential participant/proxy and answer any questions he or she asks.
- Allow the potential participant/proxy an opportunity to discuss participation with their family, friends, or family physician, if desired.
- Confirm that the participant/proxy understands the risks and benefits of participating in the study and that their participation is voluntary.
- Complete and obtain signatures for informed consent form and obtain contact information from the participant/proxy.
- Provide /send the participant/proxy with a paper/electronic copy of the signed consent form

Consent may be obtained electronically or using pen and paper consent forms, as approved by the IRB of Record.

The process of obtaining and documenting informed consent will be completed in accordance with local Good Clinical Practice recommendations. Consent procedures and forms, and the communication, transmission and storage of patient data will comply with the IRB of Record and Department of Defense requirements for compliance with The Health Insurance Portability and Accountability Act.

Upon providing informed consent, study participants will be followed for 12 months from their fracture. Given the short follow-up time, the need for a regular reassessment of consent will not apply; however, participants may withdraw their consent at any time.

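### The primary SSI and reoperation models contain treatment group alone; prespecifying a short set of injury covariates that the trial already needs would be a cheap, small improvement, not the correction of an error

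*Combined protocol and SAP*

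**What the plan says.** - **Primary and secondary models (Section 5.2.2).** "For the primary outcome, SSI will be the dependent variable and the antiseptic solution (treatment group) will be the independent variable". The sentence for reoperation is parallel. Cluster and period enter through the correlation structure, with a robust sandwich estimator.
- **Status of the model (Section 5.2.2).** It is provisional: "the final statistical modeling technique to be used will be determined in accordance with contemporary best practices prior to the completion of participant follow-up", in a separate SAP.
- **Predictors (Section 2.2).** The section names type III injury and lower-extremity fracture, and completes the list by saying that "moderate/severe wound contamination are established predictors of SSI and reoperations from the FLOW trial".
- **Availability.** Section 4.8.4 records location, severity, Gustilo class and age. Section 5.2.3 needs a contamination split, "none, minimal, or surface contamination versus contamination embedded in bone or deep soft tissues". Section 4.2 allows data on up to three open fracture regions per participant.
- **Existing adjusted analysis (Section 5.2.4, item 3).** Ten factors are listed for both outcomes. They include the four proposed below, and also method of fixation and wound closure at initial debridement. The section's opening makes the sensitivity analyses optional, while item 3 itself says that the adjusted analyses will be done.
- **Allocation and consent.** Section 4.4: "Personnel from the Methods Center will notify personnel at each participating clinical site of their treatment allocation order". Section 4.5: "The orthopaedic team (including the study coordinators) cannot be blinded to the treatment allocation". Section 7.2: "the consent process may take place up to 3 weeks post-fracture", and consent is taken "either before or after the patient has had surgery(ies) to manage their open fracture".

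**The concern.** When strong predictors are already collected, a treatment-only model gives up some power without saving any data. It also leaves the headline result open to argument if measured injury severity differs between the solutions, whether by chance or because unblinded staff enrol patients after allocation is known. A short adjusted model fixed in advance answers that argument better than one chosen after the results are seen.

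Sensitivity analysis 3 does not fill the role cleanly. Method of fixation and wound closure are decided after allocation. Section 4.8.4 treats management choices of this kind as severity markers and potential confounders, which is a reason to report them. Placed in one block with injury and patient factors, however, they make the result hard to read as a check on baseline imbalance.

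**Working it through.** **1. The plan's own figure.** Inputs from Section 5.1 and Table 5: control risk 12.5%, risk ratio 0.65 (so 8.125%), two-sided alpha 0.05, between-cluster variance 0.095. Odds ratio: (0.08125/0.91875)/(0.125/0.875) = 0.62, as in Table 5. ICC: 0.095/(0.095 + 3.29) = 0.028, also as stated.

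The two-proportion formula, n per arm = [1.96√(2p̄(1−p̄)) + 0.842√(p₁q₁ + p₂q₂)]²/(p₁−p₂)² with p̄ = 0.103125, gives 758, or 1,516 in total, against 1,400 in Table 5. Power is 76.8% at 1,400 analysed and 80.6% at 1,540. The plan used simulations whose code is not given, so I do not call this gap an error. It explains why the levels below sit near 77%. The point here is the difference between models, not the level.

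**2. Strength of the predictors (Section 1.1, reoperation rates, used as a proxy for SSI).**
- Type III, 18.0% (15.6 to 20.7): n ≈ 0.18 × 0.82/((0.207 − 0.156)/3.92)² = 872 of 2,447, about 36%. Remainder: (0.132 − 0.36 × 0.18)/0.64 = 10.5%. Odds ratio (0.18/0.82)/(0.105/0.895) = 1.87.
- Severe contamination, 29.8% (22.6 to 38.1): the same approximation gives about 134 patients (5.5%). The simulations used 5.35%, which gives a remainder of 12.3% and an odds ratio of 3.04.

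**3. Power at RR 0.65.** Logistic model with 12 cluster effects, 1,386 analysed (1,540 × 0.9), 20,000 or 40,000 replicates, both models fitted to the same data:

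| Covariates | Unadjusted | Adjusted |
|---|---|---|
| Type III and severe contamination, Section 1.1 rates | 77.2% | 78.0% |
| Same two, stronger (assumed ORs 3.0 and 4.0) | 76.8% | 78.7% |
| Proposed four, low assumed effects | 76.9% | 77.9% |
| Proposed four, high assumed effects | 76.6% | 78.6% |
| Limb and age only, low | 76.9% | 77.2% |
| Limb and age only, high | 76.6% | 77.2% |

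Assumed for the four-covariate rows, low to high: embedded contamination in 10–20% with OR 2.0–3.04; lower limb in 65% with OR 1.5–2.5; older half OR 1.2–1.5. Type III stays at 1.87.

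Other results:
- Cluster sandwich with t on 11 df, Section 1.1 rates: 68.9% to 69.7%.
- Reoperation at 13%: 78.6% to 79.4%.
- Type I error: 4.8–5.1% in every model.
- A separate simulation with 10 clusters and weak predictors (ORs 1.4, 1.2, 1.8): 76.6% to 76.7% at 1,400 analysed and 81.2% to 81.4% at 1,540. This sets the lower end of the range.
- An extreme set (ORs 4, 2.5, 4; AUC near 0.73) gave 78.1% to 81.4%. Nothing in the documents supports predictors that strong.

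**4. What happens to the odds ratio.** Unadjusted SE of the log OR at 693 per arm: √[1/(693 × 0.125 × 0.875) + 1/(693 × 0.08125 × 0.91875)] = 0.180. With the Section 1.1 predictors in the model it is 0.182. The interval widens slightly. Power rises because the conditional log OR lies further from zero.

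**5. Chance imbalance.** SE of the difference in type III share: √(2 × 0.36 × 0.64/693) = 2.58 points; 95% limit 5.05 points. Centred on 36%, the risks are 13.39% v 13.01%, a null OR of 1.03 (or 0.97 in the other direction). Case-mix variation between cluster-periods would widen the limit.

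**6. Differential grading.** Suppose there is no true difference, but 5 points more of the povidone-iodine arm are recorded as type III. The adjusted null OR becomes 0.97 (0.94 at 10 points), while the unadjusted OR stays at 1.00.

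**7. Events.** 693 × 0.125 + 693 × 0.08125 = 87 + 56 = 143, enough for four extra parameters.

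**The case against.** The strongest reply is that the plan already adjusts. Item 3 covers all four covariates, its own text commits to the analysis, and Section 5.2.2 leaves the final model to best practice. An unadjusted primary with an adjusted sensitivity analysis is a legitimate choice. That stands as a reason to rate this as optional. It does not dispose of the point: item 3 is a ten-variable model in an optional section, and it combines baseline factors with later decisions.

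The gain is also small and rests on proxies. Section 2.2 refers to moderate/severe contamination, Section 1.1 to severe contamination, and Section 5.2.3 to embedded contamination; the documents do not show these to be equivalent. Correlated predictors would shrink the gain. If all severe contamination fell within type III, the same rates would imply odds ratios of about 1.62 and 2.24, and a large-sample calculation of the gain falls from 0.86 to 0.66 points.

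The robustness argument cuts both ways. A 5-point grading difference moves the adjusted estimate about as far as the 95% limit of chance imbalance moves the unadjusted one. The documents show neither, and no section states when the grades are fixed relative to first application of the solution. This objection stands, and it is why the adjusted result should not be reported alone.

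A reader might infer that unblinded enrolment has biased the comparison, or will. The documents do not support that. They show no differential enrolment, and they contain safeguards: approach regardless of the solution received, proxy consent and classification of every screened patient (Section 4.3.1), random sampling where volume is high (4.3.2), alternation about every two months (4.4) and regular site review (4.6.5).

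**Conclusion.** The point holds as an optional improvement. The expected gain is about 0.1 to 2 points of power, 0.8 points on the Section 1.1 rates. It assumes that FLOW reoperation rates stand in for SSI, that limb, age and embedded-contamination effects lie in the ranges shown, and that the covariates are close to independent.

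Two further inferences would go too far. One is that the treatment-only analysis is invalid: it is valid under the randomisation. The other is that adjustment would tighten the reported odds ratio: it would not. The benefit lies in power, or in the precision of a standardised risk ratio or difference. Adjustment deals with measured imbalance only and cannot correct selection on unmeasured factors. The comment on item 3 stands whatever the size of the power gain.

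**What to change.** **In Section 5.2.2 or the separate SAP, before follow-up ends:**
- Prespecify adjustment of both models for Gustilo type (III v I/II), lower v upper extremity, the Section 5.2.3 contamination split, and age.
- Give a patient-level rule for several open fracture regions, for example highest Gustilo type, worst contamination and any lower-extremity region.
- Report a standardised risk ratio or risk difference.
- Show the unadjusted model and a limb-and-age-only version alongside, and state which result is primary. The limb-and-age version does not depend on unblinded grades, but gains only 0.3 to 0.6 points.

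**In Section 5.2.4, item 3:** report injury and patient factors separately from method of fixation and wound closure at initial debridement, and say which block holds time to first debridement and the emergency-department dressing.

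**Cost.** No new data; SAP text and some additional model output. The odds ratio becomes conditional, the covariates must enter the imputation model, and the adjusted estimate is exposed to differential grading. If an unadjusted primary is preferred, making the short adjusted model a firm companion analysis would keep most of the robustness benefit.

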**Table 6: Summary of Outcome Analysis Plan** 

Objective	Outcome		Hypothesis	Method of
Objective	Name	Type	Hypothesis	Analysis
To determine the effect of 10% povidone-iodine versus 4% CHG pre-operative antiseptic skin solutions on the incidence of SSI and unplanned fracture-related reoperation.	SSI	Binary	10% povidone- iodine will be more effective than CHG	Multi-level regression model
	Unplanned Fracture- Related Reoperation	Binary	10% povidone- iodine will be more effective than CHG	Multi-level regression model

**Note:** CHG = 4% chlorhexidine gluconate; SSI = Surgical Site Infection

#### 5.2.3 Subgroup Analyses

Three subgroup analyses will be performed. The primary subgroup will be defined by the severity of open fracture (Gustilo-Anderson type I or II versus III). Secondary subgroups will include: i) upper extremity versus lower extremity open fractures; and ii) none, minimal, or surface contamination versus contamination embedded in bone or deep soft tissues. These analyses will be performed by comparing the effect estimates in both groups (interaction effect). We hypothesize that effect will differ by subgroup. These analyses will be approached and reported in accordance with best practices and guidelines for subgroup analyses. **Table 7** below shows a summary of the subgroup analysis objectives, corresponding outcomes, hypotheses, and methods of analysis.

Table 7: Summary of Subgroup Analysis Plan

Objective	Outcome		Hypothesis	Method of	
Objective	Name	Type	Hypothesis	Analysis	
Primary					
Severity of open fracture (Gustilo-Anderson Type I or II vs. Type III)	SSI / Unplanned Fracture- Related Reoperation	Binary	10% povidone-iodine will be associated with a larger reduction in odds for SSI and reoperation than CHG in more severe fractures	Interaction of treatment by subgroup	
Secondary					
Upper extremity vs. lower extremity fractures	SSI /	Binary	10% povidone-iodine will be associated with a larger reduction in odds for SSI and reoperation	Interaction of treatment by subgroup	

	Unplanned Fracture- Related Reoperation		than CHG in lower extremity compared to upper extremity fractures	
None, minimal, or surface wound contamination vs. embedded wound contamination	SSI / Unplanned Fracture- Related Reoperation	Binary	10% povidone-iodine will be associated with a larger reduction in odds for SSI and reoperation than CHG in embedded contaminated wounds compared to wounds with no, minimal or surface contamination	Interaction of treatment by subgroup

**Note:** CHG = 4% chlorhexidine gluconate; SSI = Surgical Site Infection

## 5.2.4 Sensitivity Analyses

Assessment of the sensitivity or robustness of the findings to the key assumptions is essential in trials. The following sensitivity analyses may be conducted to explore the effects of alternative analysis models, alternative missing data approaches, balancing prognostic imbalance, as-treated analyses, variability in co-interventions, and alternative definitions of SSI.

- 1) *Using different analysis models:* There are several methods for analyzing cluster randomized crossover trials. Therefore, our sensitivity analyses will explore alternative multi-level models with different correlation structures for the error.
- 2) Different methods of handling missing data: There are several methods of handling missing data in trials. Multiple imputation assumes that the data are missing at random—an assumption that is not verifiable in practice. Other imputation methods will be used such as worst case scenario to impute missing data and assess the robustness of the results. For the worst case scenario analysis, we will assume that a random proportion of participants lost to follow-up experienced a study event. For this sensitivity analysis, the proportion assumed to experience a study event will be equivalent to the upper confidence interval of the observed pooled event rate for each study outcome.
- 3) Adjusted analyses for prognostic imbalance: We will also perform sensitivity analyses that assume prognostic imbalance between the two treatment groups based on the following key variables known to be risk factors for SSI or reoperation after open fracture: Gustilo fracture type, lower extremity fracture, wound contamination, time from injury to first debridement, antiseptic wound dressing in the emergency department, method of fixation, wound closure at initial debridement, age, work-related injury, and employment status.  Adjusted analyses including the above risk factors and treatment group as independent variables will be performed for the SSI and reoperation outcomes.
- 4) As-treated analyses: The proportion of surgical procedures receiving the incorrect, non-allocated antiseptic solution will be reported. "As-treated" sensitivity analyses will be performed using the solution received as the independent variable. For participants that were treated in a single open fracture surgery, they will be analyzed using the antiseptic solution received. For participants who received multiple open fracture surgeries, two analyses will be performed. First, the antiseptic solution used in their last surgery prior to a study outcome event will define their study treatment. For the second analysis, the antiseptic solution received in the majority of their

fracture surgeries will define their study treatment. Participants who were treated with multiple open fracture management surgeries, but received equal exposure to both treatment solutions (e.g. one surgery with CHG and one surgery with iodine), will be analyzed within their originally allocated treatment group.

- 5) Co-intervention variability: Selective censoring of one or more clusters and / or treatment periods will be performed to further explore between-cluster and between-period variability identified in the primary and secondary outcome comparisons. These analyses will be used to explore the robustness of the study conclusions in the context of measured practice variations in co-interventions that differ between participating sites and / or evolve over the duration of the study recruitment. Results that are sensitive to the removal of a cluster(s) and / or period(s) will be reported, along with potential clinical hypotheses that are supported by the measured clinical practice variation.
- 6) Exploratory SSI definitions: The above analyses (See Section 5.2.2) will be repeated for the primary comparison using the FRI outcome and the CDC definition within 1 year of injury to determine if the study conclusions are sensitive to alternative definitions of SSI.

**Table 8** below shows a summary of the objectives, corresponding outcomes, hypotheses, and methods for each potential sensitivity analysis.

Table 8: Summary of Sensitivity Analysis Plan

	Ohiootivo	Outcome		Hymothosis	34.1.1.64.1.	
	Objective	Name	Type	Hypothesis	Method of Analysis	
1	Different analysis models	SSI / Reoperation	Binary	10% povidone- iodine will be more effective than CHG	Multi-level regression models with different correlation structures	
2	Different missing data approach	SSI / Reoperation	Binary	10% povidone- iodine will be more effective than CHG	Multi-level regression models with missing data imputed using worst-case scenario	
3	Baseline prognostic imbalance	SSI / Reoperation	Binary	10% povidone- iodine will be more effective than CHG	Multi-level regression models with prognostic variables & treatment group	
4	As-treated analysis	SSI / Reoperation	Binary	10% povidone- iodine will be more effective than CHG	Multi-level regression models using "as treated" treatment group	
5	Co-intervention variability	SSI / Reoperation	Binary	Cluster- and period- variability is related to co-interventions	Censoring of cluster(s) and/or period(s) with differences in co- interventions	
6	Exploratory SSI definitions	FRI / CDC SSI within 1 year	Binary	10% povidone- iodine will be more effective than CHG	Multi-level regression models	

**Note:** CHG = 4% chlorhexidine gluconate; SSI = Surgical Site Infection; FRI = Fracture Related Infection; CDC = Centers for Disease Control and Prevention.

